- 2b. Feasibility and acceptability outcomes include recruitment, enrollment, and retention rates; participant satisfaction; intervention fidelity; and feasibility of assessment. We will also evaluate future implementation potential via online training platforms by developing and evaluating ten content test questions that could potentially accompany an online training module. We will assess whether the intervention condition predicts content test scores, and whether content test scores predict performance on the measures of cultural competence, communication, and trust described above.

Study results will inform the design of a multi-site RCT to test the suite of *Sign Here* training interventions and potentially validate a product of immediate value – a highly-accessible, easy-to-disseminate professional-quality training film to promote inclusion of diverse Deaf individuals in our nation’s healthcare system.

INVESTIGATOR STUDY PLAN - REQUIRED

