8. STUDY-WIDE RECRUITMENT METHODS*

N/A

9. **STUDY TIMELINES***

The total duration of the study will be 2 years and six months (see table below). Focus group participants will attend one 2-hour focus group session. Pilot RCT participants will attend one 1.5-hour study session (with up to 1 hour of pre-session work to review the intervention). Primary analyses will be completed by Year 3, Quarter 2.

Study Timeline	YEAR: QUART ER:	1				2				3	
		1	2	3	4	1	2	3	4	1	2
A i m 1	Hiring, training, and CITI certification of 4 Deaf Community Advisors										
	IRB approval and clinicaltrials.gov registration										
	Focus group recruitment, enrollment, and data collection (n = 36)										
	Qualitative analysis of focus group data										
	Film production of new Sign Here training intervention										
A i m 2	Pilot RCT preparation, IRB modification approval, and clinicaltrials.gov modification approval										
	Pilot RCT rolling recruitment, enrollment, randomization, and data collection (n = 80; recruitment rate \approx 14 participants per month)										
	Final data analyses, report/paper writing, and R01 proposal preparation										

10. **STUDY ENDPOINTS***

Aim 1a Focus Groups

After viewing the *Sign Here* prototype film, focus group participants will provide qualitative

INVESTIGATOR STUDY PLAN - REQUIRED

feedback about what they found helpful or unhelpful and concrete suggestions for improving the intervention.

Aim 2 Pilot Feasibility RCT

After randomization and receipt of the training intervention, participants will contact the research team to schedule a study session in which they will engage in **three measures of outcome**:

- At the beginning of the study session, participants will complete a **ten-question multiple choice test** to assess their understanding and retention of intervention content. *The specific content of this test will be informed by our final training intervention, so will be submitted in a Modification prior to any RCT recruitment taking place.*

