1. **Eligibility Screening.** Recruitment materials will include a link to our study's eligibility survey in REDCap. This survey will also query basic demographic characteristics, professional experience, amount of prior experience conducting informed consent, and perceived skill level for conducting informed consent procedures.
2. **Informed Consent.** For eligible participants, REDCap will immediately present a second page with informed consent information to participants via the eConsent platform.
3. **Intervention Conditions. (15 - 20 minutes).** Following eligibility screening and eConsent, REDCap will randomize participants. Our Research Liaison will then send an email to the participant with the intervention based on their assigned condition:
 - a. *Experimental condition.* Participants independently view the *Sign Here* training film.
 - b. *Intervention as usual condition.* Participants independently review a paper copy of the "NIH Guidelines on Communicating Informed Consent for Individuals who are Deaf or Hard-of-Hearing and Scientists."
4. **Scheduling Study Session.** Participants will be instructed to contact our team to schedule their study session once they have completed their intervention. When scheduling for the study session, participants will be asked to come prepared with an informed consent form that they are comfortable using for the simulation and will receive a link from the study coordinator for a virtual session using UMCMS Zoom accounts.
5. **Content Test (≈ 15 minutes).** Regardless of study condition, at the beginning of their scheduled study session, participants will complete a ten-question multiple choice test to assess their understanding and retention of intervention content.
6. **Informed Consent Simulation (≈ 1 hour).** Zoom meetings will be created to reflect a virtual healthcare appointment including informed consent procedures. When participants are sent the Zoom link for their study session, this email will also provide contact information for "Interpreter Services," as described above. The Zoom simulation will be recorded using the in-platform recording feature. At the start of the Zoom meeting, participating healthcare providers and the standardized patient will have access to virtual tools, such as auto generated captioning and the chat box function. The standardized patient will be masked to study condition.

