7. **Team Rating of Simulation.** Team members who participate in the simulation and team members who review the recording (at least three in total) will complete an evaluation following the simulation. This evaluation will assess the participant's performance conducting culturally-appropriate informed consent using validated scales of provider cultural competence (*Healthcare Provider Cultural Competency*), communication skill (*Ask, Understand, Remember Assessment*), and ability to build trust with the standardized patient/participant (*Wake Forest Physician Trust Scale*).
8. **Self-Rating of Simulation (≈ 15 minutes).** Immediately after the simulation, participants will complete a self-assessment using the validated scales described above to rate their conduct of culturally-appropriate informed consent in the simulation and are also asked to provide feedback on the study experience.

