Feasibility and acceptability outcomes include recruitment, enrollment, and retention rates; intervention fidelity; participant satisfaction; and feasibility of assessment. We will record the number of individuals screened versus enrolled and reasons for ineligibility or non-participation. We will record the number and reasons for failure to complete the interventions, and any discrepancies between RCT arms. [name] will review all intervention sessions for fidelity. Intervention engagement and participant satisfaction will be ascertained from the measures described above and discussion during the debriefing. Qualitative data regarding participant engagement and satisfaction will be analyzed using the procedures described above.

To evaluate **preliminary efficacy outcomes**, we will first examine whether there are any baseline differences between the experimental group and the intervention-as-usual group using chi-square (categorical variables) or analysis of variance (ANOVA; continuous variables). We

INVESTIGATOR STUDY PLAN - REQUIRED

will then use ANOVA to compare differences in mean scores at post-intervention between the two groups on team member ratings and self-ratings of provider cultural competence, communication skill, and ability to build trust. Effect sizes will be estimated for the primary outcomes. To calculate effect size, the difference between the two group means of an outcome will be divided by either their pooled standard deviation or by the standard deviation of the control group.

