We will also evaluate future **implementation potential** via online training platforms by evaluating the ten content test questions which could potentially accompany the *Sign Here* film as part of an online training module. We will assess whether intervention condition (dichotomous variable) predicts content test scores (continuous variable), and whether these content test scores are strongly related to real-world change on performance measures of provider cultural competence, communication skill, and ability to build trust (continuous variables). To examine the effect of the intervention on content test scores, we will compare differences in mean scores at follow-up between the two groups using ANOVA. Effect size will be estimated for content test scores. Pearson correlation analysis will be conducted to examine the strength of associations of content test scores with provider cultural competence, communication skill, and ability to build trust during the simulation encounter.

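### The Pearson correlation between content test score and simulation performance has no arm term, so on its own it cannot show whether the test tracks performance among film viewers (minor)

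*Combined protocol and SAP*

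**What the plan says.** Aim 2b (Section 4) asks "whether content test scores predict performance on the measures of cultural competence, communication, and trust". It does not restrict this to one arm.

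Section 13 (Aim 2, implementation potential) gives the method: "Pearson correlation analysis will be conducted to examine the strength of associations of content test scores with provider cultural competence, communication skill". Trust is the third measure named. The section mentions no adjustment for arm and no by-arm analysis. The stated purpose is to evaluate ten questions that might accompany the "film as part of an online training module".

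Three other statements bear on this:

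- **Who takes the test.** Section 11: "Regardless of study condition, at the beginning of their scheduled study session, participants will complete a ten-question multiple choice test".
- **What the test covers.** Section 10: "The specific content of this test will be informed by our final training intervention". The control arm receives the NIH guidance instead of the film.
- **Expected arm differences.** Section 13 plans an ANOVA of test score by arm. It also plans an ANOVA by arm of "team member ratings and self-ratings of provider cultural competence, communication skill, and ability to build trust".

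**The concern.** Test items are built around the film, only one arm sees the film, and the trial is run to find out whether the film improves performance. If the film raises both quantities, participants in the film arm sit higher on both axes and participants in the control arm sit lower on both. A single correlation over all participants then picks up that separation, even if test score says nothing about performance among people who had the same training. If the film moves the test score but not performance, the separation works the other way and dilutes a real association.

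In an online module everyone who takes the test would have watched the film. The practical question is then whether a higher score among film viewers goes with better conduct of the consent encounter. A reader who takes the pooled r as the answer could judge the test more or less useful than it is. What is at stake is the reading of one exploratory association in a pilot. No alpha, threshold or roll-out rule depends on it.

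**Working it through.** **Inputs.** N = 80 in two arms (Sections 4 and 25). The allocation ratio is not stated, so 40 per arm is assumed. The plan gives no expected correlation or arm effect. Every shift below is therefore an assumption, and there is no figure in the plan to reproduce.

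**Formula.** Let r_w be the within-arm correlation, and d1 and d2 the film-minus-control shifts in test score and performance, in within-arm SDs. With equal arms and common within-arm SDs:

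pooled r = (r_w + d1·d2/4) / √[(1 + d1²/4)(1 + d2²/4)]

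**Results.**

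| r_w | d1 / d2 | Calculation | Pooled r |
|---|---|---|---|
| 0 | 0.8 / 0.8 | 0.16 / 1.16 | 0.14 |
| 0 | 2.0 / 1.0 | 0.50 / √(2 × 1.25) | 0.32 |
| 0.30 | 0.5 / 0.5 | 0.3625 / 1.0625 | 0.34 |
| 0.30 | 0.8 / 0.8 | 0.46 / 1.16 | 0.40 |
| 0.30 | 2.0 / 1.0 | 0.80 / √(2 × 1.25) | 0.51 |
| 0.30 | 2.0 / 0.2 | 0.40 / √(2 × 1.01) | 0.28 |
| 0.30 | 2.0 / 0 | 0.30 / √2 | 0.21 |
| 0.30 | 0.8 / −0.3 | 0.24 / √(1.16 × 1.0225) | 0.22 |

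The error can go in either direction. If neither variable shifts by arm, pooled and within-arm r agree.

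**Size against sampling error.** Fisher 95% CIs at n = 80 are 0.13 to 0.52 around 0.34, and 0.19 to 0.57 around 0.40. Both contain 0.30, so under modest shifts the distortion is smaller than the noise.

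**What adjustment for arm does.** In 20,000 simulated trials with 40 per arm and r_w = 0, the arm-adjusted correlation averaged about 0.00 at every shift tried. The pooled r averaged 0.11 at 1.0/0.5 and 0.32 at 2.0/1.0.

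**Precision of the alternatives at r = 0.30.**

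- Film arm alone, n = 40: tanh(0.3095 ± 1.96/√37) = −0.01 to 0.56.
- Partial correlation, n = 80, one covariate: tanh(0.3095 ± 1.96/√76) = 0.08 to 0.49.

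**When the arms differ.** With shifts of 0.8/0.8, a film-arm r of 0.50 with a control-arm r of 0.10 has a mean within-arm r of 0.30. The pooled r is 0.40 and the partial r 0.30. Swapping the arms gives the same two numbers. Only the within-arm correlations separate the two cases.

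**The case against.** The strongest reply is that the plan answers the question it asks. Aim 2b asks whether test scores predict performance, with no restriction to film viewers, and the pooled r describes exactly that. A content test is also commonly judged over a range of knowledge, and two arms supply that range. If the film improves performance by improving knowledge, part of the between-arm association is the link the plan wants to see. All of this stands, and it is why the pooled r should stay.

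A reader might go further and infer that the film-arm correlation should replace the pooled one. The documents do not name film viewers as the target; that is a reasonable inference from the online-module purpose. Nor is the film-arm r generally more accurate. In simulations with a common within-arm r of 0.30, its root-mean-square error for the film-viewer association was 0.146 against 0.107 for the pooled r at 0.5/0.5, and 0.145 against 0.135 at 0.8/0.8. It did better at 2.0/1.0 (0.147 against 0.222). The partial correlation, at about 0.10, had the lowest error in all of these, but they assume the same association in both arms. Film-arm scores may also cluster near the top of a ten-item test, which would attenuate the film-arm r.

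A reader might also infer that the analysis set is undefined. Section 13 names none, but both arms take the test and no exclusion is given, so the natural reading is everyone. That Section 13 does not say whether this correlation uses team ratings, self-ratings or both is likewise a missing detail.

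**Conclusion.** The point holds as a minor, inexpensive improvement. The planned correlation has no arm term, and read naturally as pooled it mixes between-arm shifts with the association among people given the same training. The distortion is small for modest arm effects (0.30 becomes 0.34 at 0.5/0.5). It is large only if the film moves the test score strongly: to 0.51 if performance also shifts by 1 SD, or down to 0.21 if performance does not shift at all. These sizes rest on assumed shifts, equal arms and common within-arm SDs.

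A reader might infer that the pooled analysis is invalid or that the trial's conclusions are at risk. The documents do not support that. The pooled r is a valid description of the mixed sample, and arm is recorded, so the adjusted value can be computed from the same data.

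**What to change.** In Section 13, keep the Pearson sentence and add after it:

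> *For each performance measure we will also report the partial correlation with content test score over both arms, controlling for study arm, with a 95% CI. Correlations within each arm will be reported with 95% CIs as descriptive checks on whether the association is similar in the two arms. The unadjusted correlation over both arms describes the whole sample. All are estimates, not tests.*

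The addition should not refer to a rule for combining raters. Section 11 says that those in the simulation and "team members who review the recording (at least three in total) will complete an evaluation following the simulation", but Section 13 states no combining rule.

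**Cost.** A few sentences and no new data. Each pairing of test score with a measure yields four coefficients (pooled, partial, two within-arm): 3 × 4 = 12 for one rating source, 24 if team and self-ratings are both used.

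**Downsides.**

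- The within-arm estimates are imprecise, with the interval shown above.
- The partial correlation represents film viewers only if the association is similar in both arms, which the documents do not establish.
- Adjusting for arm removes between-arm differences in knowledge that may be part of how the film works, which is why the pooled r is kept beside it.

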14. PROVISIONS TO MONITOR THE DATA TO ENSURE THE SAFETY OF SUBJECTS*

Focus group participants will attend one 2-hour focus group session. Pilot RCT participants will attend one 1.5-hour study session (with up to 1 hour of pre-session work to review the intervention). During these sessions, every possible effort will be made to ensure the safety of participants. Any adverse events will be reported to the UMCMS Institutional Review Board.

Although highly unlikely, there is minimal risk that the participant may experience feelings of discomfort or situational psychological distress while viewing the *Sign Here* intervention, discussing the *Sign Here* intervention, or participating in the informed consent simulation. (Note: This reaction was not reported by any of the participants in our preliminary research efforts.) Should a participant's distress become severe or continue beyond the completion of the study, subjects will be encouraged to contact PI [name], who can provide additional debriefing to the participant and, if needed, refer the participant to a qualified mental health provider.

15. WITHDRAWAL OF SUBJECTS WITHOUT THEIR CONSENT*

It is highly unlikely that we will need to withdraw participants from either the Aim 1a focus groups or the Aim 2 pilot RCT. Participants will only be withdrawn if they pose harm to themselves or others (i.e., physical aggression, verbal threats). Although this reaction is highly unlikely, should it occur, PI [name] would debrief the participant and provide referral to crisis or therapy services outside of the research study as needed.

16. RISKS TO SUBJECTS*

Any serious adverse events, unanticipated problems, or breaches of confidentiality that occur will be reported to the UMCMS Institutional Review Board and the NIDCD project officer

INVESTIGATOR STUDY PLAN - REQUIRED

within 48 hours. Additionally, an annual report will be submitted to the NIDCD project officer summarizing all adverse events.

Aim 1a Focus Groups

The proposed focus group study poses no more than minimal risk. There is a potential risk of loss of confidentiality. There is a potential risk of discomfort or situational psychological distress. The proposed study poses no more than minimal risk. There is a potential risk of loss of confidentiality. We address each, in turn, below:

Risks associated with potential loss of confidentiality. There is a slight risk that research records (i.e., video recordings) might be obtained by unauthorized persons. There is a slight risk that research data files might be compromised and obtained or viewed by unauthorized persons. Our procedures for protecting against such risks are described in Section 26.

Risks associated with situational psychological distress. Although highly unlikely, there is minimal risk that participants may experience feelings of discomfort or situational psychological distress when viewing the *Sign Here* prototype intervention. However, this reaction was not reported by any of the participants in our preliminary research efforts. Every possible effort will be made to ensure the safety of participants. Any adverse events will be reported to the UMCMS Institutional Review Board. Although highly unlikely, there is minimal risk that the participant may experience feelings of discomfort or situational psychological distress when viewing or discussing the *Sign Here* prototype intervention. (Note: This reaction was not reported by any of the participants in our preliminary research efforts.) Should a participant's distress become severe or continue beyond the completion of the study, participants will be encouraged to contact PI [name], who can provide debriefing to the participant and, if needed, refer the participant to a qualified mental health provider.

Aim 2 Pilot Feasibility RCT

The proposed study pilot RCT poses no more than minimal risk. There is a potential risk of loss of confidentiality. There is a potential risk of discomfort or situational psychological distress. We address each, in turn, below:

Risks associated with potential loss of confidentiality. There is a slight risk that research records (i.e., video recordings, written evaluations) might be obtained by unauthorized persons. There is a slight risk that research data files might be compromised and obtained or viewed by unauthorized persons. Our procedures for protecting against such risks are described in Section 26.

Risks associated with situational psychological distress. Although highly unlikely, there is minimal risk that participants may experience feelings of discomfort or situational psychological distress while viewing the *Sign Here* intervention or participating in the informed consent simulation. However, this reaction was not reported by any of the participants in our preliminary research efforts. Every possible effort will be made to ensure the safety of participants. Any adverse events will be reported to the UMCMS Institutional Review Board. Should a

INVESTIGATOR STUDY PLAN - REQUIRED

participant's distress become severe or continue beyond the completion of the study, subjects will be encouraged to contact PI [name], who can provide additional debriefing to the participant and, if needed, refer the participant to a qualified mental health provider.

17. POTENTIAL DIRECT BENEFITS TO SUBJECTS*

Aim 1a Focus Groups

The following potential benefits cannot be guaranteed. Potential benefits to focus group participants include:

- Increased knowledge about how to conduct research informed consent with Deaf individuals.
- The chance to provide valuable feedback on the development of two innovative training interventions.

Aim 2 Pilot Feasibility RCT

The following potential benefits cannot be guaranteed. Potential benefits to pilot RCT participants include:

- Increased knowledge about how to conduct informed consent with Deaf individuals.
- The chance to learn directly from Deaf community members and researchers and provide valuable feedback on innovative training interventions.

18. VULNERABLE POPULATIONS*

We will not specifically recruit members of vulnerable populations. We will not knowingly include pregnant women as participants; however, we will not assess participants' pregnancy status.

19. MULTI-SITE RESEARCH*

N/A

20. COMMUNITY-BASED PARTICIPATORY RESEARCH*

Community-based participatory research is a central value in the planning and execution of the proposed study. In a parallel process between our research topic and research process, we aim to embody the purposes of informed consent by adopting research methods that respect Deaf people's rights, support Deaf people's autonomy and decision-making, and build trust with the Deaf community:

- Our team is **Deaf-led**. The leadership team includes two Deaf co-investigators, a significant feat given that only 1% of science and engineering doctorates are earned by Deaf or hard-of-hearing individuals.
- Our methods are **Deaf-informed**. We will hire four Deaf Community Advisors, laypersons

INVESTIGATOR STUDY PLAN - REQUIRED

from the Deaf community, to serve as active members of the team who will guide day-to-day methodological decisions to ensure they align with the diverse experiences, perspectives, and needs of the Deaf community.

